8.1 Primary Objective

The primary objective measure will be to compare the total number of metaphase II (MII) oocytes between the two groups.

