11.2 Randomization

This is a prospective superiority randomized pilot study. Patients will be randomized to either control group (Group A) or double trigger group (Group B), on the day of triggering, only after patient eligibility has been established and patient consent has been obtained. Randomization sequence and allocation will be created using a computer-generated randomization list, using 1:1 allocation.

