12.1 Treatments Administered

A single injection of 150mcg of corifollitropin alfa will be administrated at day 2/3 of the cycle, followed by 225IU of recombinant FSH (rFSH) in a fixed antagonist protocol. Cycle monitoring will be performed through serum estradiol (E2), progesterone and luteinizing hormone (LH) assessments, and serial transvaginal ultrasound examinations. The study will include exclusively patients with ≤ 9 follicles ≥ 11 mm on the day of triggering. Therefore, patients will be randomly allocated in two groups: Group A (control group) will undergo conventional triggering with hCG 5000 IU and a single oocyte retrieval (OR) will be performed 36 hours later; Group B (study group) will undergo triggering with GnRHa 0,2ml and a first OR will be performed 36 hours later. In both groups, triggering will be performed if two or more follicles ≥ 17 mm are observed and all follicles >10 mm will be aspirated, in line with current clinical practice (Nivet et al., 2016). In Group B (study group), 225 IU of rFSH will continue after the first trigger. Antagonist administration will be initiated when at least one follicle measuring ≥ 14 mm will be present in the ultrasound. If one or more follicles ≥ 17 mm are observed, patients will undergo a second triggering with hCG 5000 IU and a second OR will be performed. In case of patients with no follicular development following 13 additional days of rFSH, the cycle will be cancelled. Metaphase II (MII) oocytes will then be injected according to standard ICSI procedure. In the control group a fresh single/double embryo transfer will be performed

according to clinical practice (day 3 or day 5). For the study group, a freeze-all strategy will be applied, followed by a transfer of a maximum two embryos in an artificially prepared frozen-thawed cycle (overview of all procedures: tables and figures, fig.2).

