12.3 Randomization and Stratification

Patients will be randomized to either control group (Group A) or double trigger group (Group B), on the day of triggering, only after patient eligibility has been established and patient consent has been obtained. Only patients with ≤ 9 follicles of ≥ 11 mm will be included. Randomization sequence and allocation will be created using a computer generated randomization list, using 1:1 allocation.

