15.3 Statistical Considerations and Data Analysis

Analyses were performed in intent-to-treat fashion and per-protocol. Consequently, in the intention-to-treat analysis, all patients will be included in the final analysis as long as after fulfillment of the inclusion criteria they were randomly allocated to one of the treatment groups, whereas the per-protocol analysis will include only those patients who completed the treatment originally allocated. Continuous data will be presented as mean \pm SD or median [range] and categorical data will be described by number of cases, including numerator and denominator, and percentages, in line with the CONSORT statement (www.consort-statement.org). Categorical data and continuous data that do not show a normal distribution will be analyzed by Pearson's χ^2 test/Fisher exact test or Mann-Whitney's U test as appropriate.

The normality of the distributions will be assessed with Kolmogorov-Smirnov's test and graphical methods. All tests will be two-sided. Differences will be considered as statistically significant if the null hypothesis could be rejected with $>95\%$ confidence ($p<0.05$). All tests will be performed with the STATA version 13.

Power/Sample Size:

Our sample size of 46 patients (23 per group) has a power of at least 90% to detect superiority of the double trigger group (mean 5.4 MII) versus control group (mean 3.4 MII), standard deviation ($SD=2$), using a two-sided, t test, at significance level alpha of 0.05.

16. Ethical Considerations

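### The primary MII comparison has no fixed test or effect measure and ignores the follicle count that every woman must have before randomisation

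*Combined protocol and SAP*

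**What the plan says.** The primary outcome is set in section 8.1: "The primary objective measure will be to compare the total number of metaphase II (MII) oocytes between the two groups". Section 15.3 has no analysis paragraph specific to it. One generic rule covers all continuous outcomes: group summaries are means with SDs or medians with ranges, and "The normality of the distributions will be assessed with Kolmogorov-Smirnov's test and graphical methods". The fallback sentence begins "Categorical data and continuous data that do not show a normal distribution will be analyzed by" and leads, for continuous data, to Mann-Whitney. No test is named there for data that pass. The t test appears only in the power statement (section 15.3 and the synopsis), "using a two-sided, t test, at significance level alpha of 0.05". No covariate, regression model, between-group estimate or confidence interval is given for MII.

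Section 12.1 states: "The study will include exclusively patients with ≤ 9 follicles ≥ 11 mm on the day of triggering". Section 12.3 repeats it: "Only patients with ≤ 9 follicles of ≥ 11 mm will be included". Section 11.2 places randomisation "on the day of triggering, only after patient eligibility has been established and patient consent has been obtained". Table 1 marks an eligibility check at the final maturation trigger in both groups. Section 12.3 has stratification in its heading but names no stratification factor.

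**The concern.** Two features of the plan meet in the primary comparison.

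First, the test and the way the result is expressed depend on a data-driven check that is not fully defined. The Kolmogorov-Smirnov variant is not stated, nor whether it is applied by arm, to pooled data or to residuals, and reading plots is a matter of judgement. The trial could report a mean difference, or a rank test with medians. Only the first can be set directly against the planned difference of 2.0 MII. For a pilot, whose size estimate will be carried forward, that matters more than the p-value.

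Second, a covariate fixed before allocation is left unused. Section 12.1 has all follicles above 10 mm aspirated at retrieval, so the trigger-day count of follicles of 11 mm or more describes largely the follicles that supply the first-retrieval oocytes. With 46 women and no stratification, neither the design nor the analysis deals with chance imbalance in that count.

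**Working it through.** **Inputs from the documents.** Means 5.4 and 3.4 MII (difference 2.0), common SD 2, 23 per arm, two-sided alpha 0.05, t test (section 15.3).

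**Assumed, because the documents do not give it.** The within-arm correlation r between the count and total MII, taken as 0 to 0.6.

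**1. The plan's own figure.** Noncentrality = 2.0 / (2 × √(2/23)) = 2.0 / 0.590 = 3.39. With 44 degrees of freedom the critical value is 2.015 and power is 91.2%. At 22 per arm it is 89.97%, so 23 is the smallest number per arm reaching 90%. The stated figure is reproduced.

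**2. Adjusting for the count.** Residual SD = 2 × √(1 − r²), with 43 degrees of freedom. The simulation used 20,000 runs, with MII rounded to integers and floored at 0, the count an integer from 2 to 9, and HC2 standard errors.

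| r | Residual SD | Power, formula | Power, simulated |
|---|---|---|---|
| 0 | 2.00 | 91.2% | 90.3% |
| 0.3 | 1.91 | 93.5% | 92.4% |
| 0.4 | 1.83 | 95.1% | 94.0% |
| 0.6 | 1.60 | 98.5% | 97.8% |

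The unadjusted t test in the same simulations had power of 90.7–91.2%. The simulated 95% CI half-width was 1.17 oocytes unadjusted and 1.13, 1.09 and 0.96 at r = 0.3, 0.4 and 0.6. The unadjusted formula gives 2.015 × 0.590 = 1.19; flooring and rounding explain the small gap. Type I error was 4.9–5.2% with HC2 and 4.3–4.5% with HC3.

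**3. If Group B is more variable.** Suppose, as an assumption, that the second retrieval adds independent variance 2. Group B's variance is then 4 + 2 = 6 (SD 2.45) and the average variance of the two arms is (4 + 6)/2 = 5. Unadjusted power is 84.3%.

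- Count predicts first-retrieval yield only: residual variance 4(1 − r²) + 1. Power is 86.8%, 88.8%, 91.2% and 94.0% at r = 0.3, 0.4, 0.5 and 0.6. Simulated HC2 values at 0.4 and 0.6 are 87.6% and 93.0%.
- Count predicts the total: residual variance 5(1 − r²). Power is 87.4%, 89.9%, 92.8% and 96.0%.

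**4. The normality gate.** With integer MII at SD 2 and 23 per arm, plain Kolmogorov-Smirnov (parameters estimated from the data, no correction) rejects in at least one arm in 1.0–1.4% of trials. The Lilliefors-corrected version rejects in 56–59%. A separate simulation that also used Poisson counts found about 1–4% and 59–75%. Power was 90–91% for the t test and 89% for Mann-Whitney. The two disagreed on significance in about 3% of trials with a true difference of 2.0. Type I error of the two-stage rule was 3.9–5.4%. The gate therefore barely affects error rates; what it changes is which result is reported.

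**The case against.** The strongest reply is that nothing stated is wrong. The unadjusted comparison is unbiased, meets its power target and matches the test used for sizing, which is a legitimate choice in a single-centre pilot. All of that stands.

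The gain also rests on an unknown r, and the cap at 9 follicles may keep it low. At r = 0.1 or 0.2 the formula gives only 91.5% or 92.3%. In Group B the second retrieval is meant to harvest follicles that were small at the first, some below the 11 mm threshold, so its yield might even run against the count. Taking correlations of 0.3 for the first retrieval and −0.3 for the second, simulated power moved only from 85.2% to 85.7%. This limits the expected benefit, but even here adjustment does no harm.

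On the gate, the plan names Kolmogorov-Smirnov and not Lilliefors. On the literal reading a switch is rare, and the t test can be inferred from the power statement. Graphs also enter the decision, so neither rejection rate describes it exactly. This is fair, but it confirms that the choice rests on unstated details, and an inferred test still supplies no between-group estimate or interval.

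Finally, Table 1 schedules ultrasound with follicle measurement, and the synopsis lists preovulatory follicles as an endpoint, so the count may already be recorded in some form. However, Table 1 does not mark ultrasound in the trigger column, so the covariate has to say which scan it comes from.

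**Conclusion.** The point holds as an improvement worth making; it is not an error that invalidates the trial. That section 15.3 fixes no primary test, effect measure or interval for MII follows from the text and does not depend on r.

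The precision gain does depend on r. At SD 2 it is about 2 points of power at r = 0.3, 4 at r = 0.4 and 7 at r = 0.6 by formula, with a CI narrower by 0.04 to 0.21 oocytes on each side. It is larger if Group B is more variable than planned: from 84% to about 87% at r = 0.3, and to 89–94% at r = 0.4–0.6 if the count predicts only the first retrieval. The possible loss is about 1 point if the count predicts nothing. Confidence is medium, because r and Group B's SD are assumptions.

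**What to change.** In section 15.3, pre-specify one primary analysis in the intention-to-treat population: linear regression of total MII on arm and the count of follicles of 11 mm or more used to confirm eligibility, with HC2 standard errors, reporting the adjusted mean difference and its 95% CI. Define the count as that from the last scan before randomisation.

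Remove the normality check as a gate for the primary outcome. Report the unadjusted t test and Mann-Whitney as sensitivity analyses whatever the distribution looks like. Keep the power statement ("Our sample size of 46 patients (23 per group) has a power of at least 90" per cent) and label it as the power of the unadjusted t test at SD 2.

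The cost is SAP wording, one STATA command and an explicit eCRF field for the count, since the documents do not list it as a recorded item. No extra patients, visits or measurements are needed. The downsides are a model-adjusted headline estimate and the loss of about 1 point of power if the count proves unrelated to MII.

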16.1 Ethical conduct of the study

16.1.1 Declaration of Helsinki

The study protocol will follow the ethical principle established in the declaration of Helsinki.

16.1.2 Ethics Committee

The protocol will be submitted to the local Ethics Committees of Universitair Ziekenhuis Brussel. Strict confidentiality of all personal and research data will be ensured.

No specific reimbursement will be given to patients participating in the study.

The informed consents were written in Dutch, French and English.

16.3 Patient and Study Data Protection

Participation in this study is voluntary and women are free to withdraw from the study at any time and for any reason without prejudice.

All information about the treatment received during the study remains confidential.

The subjects name and any data related to her identity will not be disclosed when the results of the study will be published for scientific purposes.

Access to the medical record and information obtained regarding participation in the trial will be limited to the study staff, the Ethics Committee and the health authorities.

The investigator will never reveal the subjects name in the context of a publication or conference but he/she will also encode (the identity will be replaced by an ID code in the study) the data before sending them to the manager of the database of collected data. The investigator and his/her team will therefore be the only ones to be able to establish a link between the data transmitted throughout the study and the medical records. For the study data manager designated by the head investigator, the data transmitted will not allow the subject to be identified. The latter is responsible for collecting the data gathered by all investigators taking part in the study, processing them and protecting them in accordance with the requirements of the Belgian law on the protection of privacy and by the law on patient's rights of 22 August 2002.

The new European General Data Protection Regulation (GDPR), in force since 25 May 2018, imposes additional requirements on how companies or organizations may use personal data. One of these requirements is that the data controller provides the following information.

As also indicated in the informed consent form, personal data are collected in the context of the investigation in which the subject participates. The sponsor is responsible for the correct processing and the information obligation that goes with it.

In addition to the personal data, such as data on age and sex, 'special categories' of personal data are also collected (such as ethnic background, state of health and medical conditions, including medical history, treatments and response to treatments, biological samples, e.g. blood samples, tissue, and the results of their analysis, medical imagery, e.g. scans, x-rays, and the results of their evaluation).

Of course, personal data may only be used for the scientific research purposes described in the form for informed consent.

The data may be accessed by persons located in countries that do not use the same standards of legal data protection as the EU. The conditions of the European and Belgian legislation on the protection of personal data must be respected.

In accordance with the relevant legislation, the data collected as part of the research will be kept for at least 20 years, or 30 years if these data are also part of the medical file.

According to the GDPR, the subject has a number of rights regarding the processing of the data. If any further questions about this, the subject can always contact the investigator.

The data protection officer of the research department is also available for contact details: DPO (data protection officer) via [contact] The subject also has the right to submit a complaint about how the information is handled. This can be done with the Belgian supervisory authority responsible for enforcing data protection legislation.

16.4 Subject Identification

Every woman will be identified by a study specific subject number.

16.5 Conflict of Interest

There are no conflicts of interest to declare.

17. Finance and Insurance

If the patient will decide to take part in this study, this will not involve any extra costs for her or her insurer. The additional costs of the study (extra medication for prolonged stimulation, ovum pick-up, additional sampling) will be covered by funding from MSD.

Any participation in a clinical study involves a risk, however small it is. Even if there is no fault, the investigator accepts responsibility for damage caused to the participant (or in the event of death, his/her dependents) and directly or indirectly linked to his/her participation in the study. The sponsor has taken out insurance for this responsibility.

18. Reporting and Dissemination

Missing efficacy and safety outcomes will be considered as negative, regardless of the cause which may justify the lack of said information (e.g. cycle cancelled due to the survival after warming of no embryo or loss to follow-up). These patients will be included in the analysis following the ITT principle.

19. Conflict of interest statement

This study is financially supported by MSD.

None of the other investigators have conflict of interest to declare.

20. Tables and Figures

Fig. 1 study design

[figure not shown]

Table 1: Summarizing table of all investigations and procedures

Group A (control group)

	Day 2 of the cycle	Day 8 of the stimulation	Every 1 or 2 days	Final maturation trigger	Ovum pick-up*	Day 3 or 5 after egg retrieval	12 days after embryo transfer
Informed consent	x						
Inclusion/exclusion criteria	x			x			
Infertility/menstrual/reproductive history	x						
Blood sample for endocrine monitoring (LH, FSH, estradiol, progesteron)	x	x	x		x		
Ultrasound with follicle measurement		x	x				
Embryo transfer						x	
Blood sample for pregnancy hormone (hCG)							x

(*) with collection of follicular fluid and cumulus cells

	Day 2 of the cycle	Day 8 of the stimulation	Every 1 or 2 days	Final maturation trigger	1 st Ovum pick-up* with freezing of all embryos	4 days after first pick-up and 3-4 times after that	2 nd Ovum pick-up* with freezing of all embryos	In the next cycle
Informed consent	x							
Inclusion/exclusion criteria	x			x				
Infertility/menstrual/reproductive history	x							
Blood sample for endocrine monitoring (LH, FSH, estradiol, progesteron)	x	x	x		x	x	x	
Ultrasound with follicle measurement		x	x			x		
Embryo transfer								x

